11.1 Subject Disposition

Different variables from the eCRF will be considered to determine the number of patients who reached the various stages of the study, and those who dropped out and for what reasons. These variables will be:

- Date of Informed Consent (Consent form)
- Date of Admission to study/treatment hospital (Pre-procedure form)
- Date of first slice/imaging (Pre-procedure form)
- Date of Endovascular treatment (Procedure form)
- Date of 24 hour post-treatment assessment (24 Hrs Post-Procedure form)
- For angiography screen failures, Date of 72 hour post-treatment assessment (72 Hours Follow-up form)
- Date of 7 day follow-up (Discharge/ 7 Days Post-Procedure form)
- Date of discharge (Discharge/ 7 Days Post-Procedure form)
- Date of 90 day follow-up (90 Days Follow-up form)
- Date of Scan (Imaging Adjudication form)
- Date of EOS Evaluation (End of Study form)
- Date of Death (General form / CEC form)

Corresponding summaries will be presented as the number and percentage of patients who reached each stage of the study, with a graphical display plotting running totals reaching each stage over time.

11.2 Protocol Deviations

A protocol violation is defined as an event that resulted in an increased risk to a subject or others; affected the right, safety or welfare of a subject; or affected the integrity of the study. Protocol violations include, but are not limited to:

- Failure to obtain informed consent prior to patient enrolment
- Enrolled patient did not meet the inclusion/exclusion criteria
- Source data permanently lost
- Introduction of rescue therapy prior to attempting revascularization with EmboTrap for three passes.

Any other events that do not comply with the requirements of the protocol will be considered protocol deviations. Protocol deviations include, but are not limited to:

- Incorrect version of the informed consent form used
- Patient did not attend follow-up visit or follow-up visit was outside the required window

In the case that any violations or deviations occur, a summary of the total number and proportions of each type along with a brief explanation will be presented in the clinical study report.

11.3 Inclusion and Exclusion Criteria

A listing will be generated showing the number and percentage of subjects that fulfilled the inclusion and exclusion criteria listed in sections 6.2 and 6.3 of the CIP002 rev 05.

12 Demographic and Baseline variables

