Endovascular mechanical revascularization (thrombectomy) is an increasingly used method for intracranial large vessel recanalization in acute ischaemic stroke. Currently, a number of mechanical recanalization devices are in clinical use. First generation devices included the Merci Retriever device. Newer devices based on stent-like technology, referred to as “stentriever” or “stent- retrievers”, have displaced these first generation thrombectomy devices for recanalization in acute ischemic stroke secondary to large vessel occlusion.

The EmboTrap® Revascularization Device (hereafter referred to as the EmboTrap device) has been developed and CE approved for this indication in Europe. The EmboTrap device is approved for use in the US strictly within the confines of the ARISE II IDE Study. It is indicated for use in the anterior and posterior neurovasculature in vessels such as the internal carotid artery, the M1 and M2 segments of the middle cerebral artery, the vertebral artery, and the basilar artery.

This study is designed to show non-inferiority to devices already approved for use on the US market and thereby supply clinical data in support of a 510k application for regulatory approval in the United States

The structure and content of this statistical analysis plan (SAP) provides sufficient detail to meet all the requirements in accordance with the International Conference on Harmonisation guidance of Statistical Principles in Clinical Trials (ICH E9). All work planned and reported for this SAP will follow internationally accepted guidelines. The following documents were reviewed in the preparation of this SAP:

- Clinical Research Protocol CIP002*
 - rev 03 issued 19th June 2015
 - rev 05 issued 28th June 2016
- Case Report Forms (eCRFs).
- ICH E9 and E3

The reader of this SAP is encouraged to also read the clinical protocol for details on the conduct of this study, and the operational aspects of clinical assessments and timing for completing a patient in this study.

* Note: Patients were only enrolled and treated under two revisions of the ARISE II study protocol; revision 03 and revision 05. The differences affecting data analyses in these versions relate to;

- Device of a longer length added during the study to provide an additional choice.
- Amendment of inclusion criterion #10 and exclusion criterion #15.
- Revision in the definition of rescue therapy.

4 Purpose of SAP

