7.1 Missing and Censored Data

An extra 30% to the required evaluable patient cohort number is included to bring the total cohort to 228. Missing data will be examined, and the reasons will be investigated and reported.

Missing data for the primary endpoint might be expected in the case of patients eligible for treatment (ITT) but receiving no treatment and thus would have no angiography during procedure from which to make a determination of mTICI. For the primary efficacy outcome, a simple sensitivity analysis of the ITT population will be carried out to assess the robustness

of the conclusions on this endpoint to missing data (see Section 10.3). No missing data is expected for the primary safety outcome and no imputation will be performed for missing data on secondary outcomes. Results measured outside the protocol prescribed time windows, will be treated as missing data.

8 *Timing of analyses*

8.1 *Interim analyses*

There are no planned interim analyses for this study.

8.2 *Final analyses*

All final analyses identified in this SAP will be performed after the last patient has completed the study. Before carrying out the analyses, the data management team is responsible for the database cleaning process to ensure the integrity of the analyses. No database may be locked or analyses completed until the SAP has been approved and the database will be locked prior to the initiation of the analysis. Key statistics and study results will be made available following database lock and prior to completion of the final Clinical Study Report (CSR).

Any post-hoc exploratory analyses completed to support planned study analyses, which were not identified in this SAP, will be documented and reported in appendices to the CSR.

9 *Analysis populations*

The primary efficacy endpoint will be examined for the following cohorts, An Intention to Treat cohort, a modified Intention To Treat cohort created to select a data set relevant to FDA lytic labelling constraints relevant at the time of study execution, a Per Protocol cohort, and a Treated Set cohort, which mirrors the protocol, and excludes any violations. The primary population for test will be the ITT.

9.1 *Intention to Treat*

Intention to Treat (ITT): Will include all patients who meet all angiographic eligibility criteria.

- The primary analysis for the primary efficacy endpoint will be performed on subjects in the ITT cohort with non-missing mTICI assessments.

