Per Protocol (PP): Defines a cohort of subjects who meet all eligibility criteria and are treated with the Embotrap device. Patients with protocol violations will be excluded from analysis.

In order to provide additional context to the results observed in the ITT cohort,

- The analysis of the primary efficacy endpoint will be repeated on patients in the PP cohort with non-missing mTICI assessments.
- The analysis of the primary safety endpoint will be repeated on patients in the PP cohort.

9.4 *Treated Set*

Treated Set (TS): Defines a cohort of subjects who are treated with the EmboTrap device regardless of study eligibility. In order to provide additional context to the results observed in the ITT cohort,

- The analysis of the primary efficacy endpoint will be repeated on patients in the TS set with non-missing mTICI assessments.
- The analysis of the primary safety endpoint will be repeated on patients in the TS set.

10 General issues for Statistical Analysis

10.1 *Software used for the analysis*

All Primary and secondary statistical analyses will be validated by an independent statistician, or using independent software (R, SAS, SPSS, Minitab or Stata). All of the code generated will be kept by both the study statistician and the independent statistician.

10.2 *Confidence intervals*

All confidence intervals reported for binary variables will be Wilson exact binomial confidence intervals and for continuous variables will be based on a normal distribution assumption for the parameter of interest.

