13.4.3 Analysis of protocol version subjects were enrolled under

Patients were only enrolled and treated under two revisions of the ARISE II study protocol; revision 03 (issued 19th June 2015) and revision 05 (issued 28th June 2016). The differences affecting data analyses in these versions relate to;

- additional length of device added as a choice
- amendment of inclusion criterion #10 and exclusion criterion #15
- revision in the definition of rescue therapy

An extra analysis of the primary outcome will be undertaken to determine if there is any difference between data from subjects enrolled under revision 03 of the protocol and data from those enrolled under revision 05 of the protocol.

14 Safety Analyses

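### SAP 11.3 judges every subject's eligibility by the rev 05 criteria, although some subjects were enrolled under rev 03 with a different inclusion criterion 10 and exclusion criterion 15

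*SAP*

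**What the plan says.** Four parts of the SAP bear on this point.

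- **Two revisions.** The Preface (SAP section 3) says "Patients were only enrolled and treated under two revisions of the ARISE II study protocol; revision 03 and revision 05". Among the differences that it says affect the analyses it lists "Amendment of inclusion criterion #10 and exclusion criterion #15". SAP 13.4.3 repeats this and gives the issue dates: 19 June 2015 for rev 03 and 28 June 2016 for rev 05.
- **Eligibility listing.** SAP 11.3 counts the subjects who "fulfilled the inclusion and exclusion criteria listed in sections 6.2 and 6.3 of the CIP002 rev 05". It makes no exception for subjects enrolled under rev 03.
- **Violations.** SAP 11.2 includes among protocol violations: "Enrolled patient did not meet the inclusion/exclusion criteria". No revision is named.
- **Per-protocol set.** SAP 9.3: "Defines a cohort of subjects who meet all eligibility criteria and are treated with the Embotrap device". It adds: "Patients with protocol violations will be excluded from analysis". Again no revision is named.

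The ITT set, on which the primary test is done, is defined differently in SAP 9.1: "Will include all patients who meet all angiographic eligibility criteria".

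**The concern.** A subject can only be expected to meet the criteria in force at enrolment. Criterion 10 concerns the baseline CT or MRI assessment of the infarct, and criterion 15 concerns blood pressure. Both changed between the two revisions that recruited. A listing that applies the later text to everyone does not report whether rev 03 subjects were properly enrolled.

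The wider exposure comes from SAP 9.3 and 11.2. Both turn on eligibility and neither says which text defines it. The only criteria list that the SAP points to is the rev 05 one, and rev 05 is the only protocol appended (Appendix 1). A programmer building the per-protocol flag could reasonably use it. The violation count and the per-protocol repeats of the primary efficacy and primary safety analyses would then depend on a rule that did not apply to part of the cohort. Protocol 5.3 adds to the need for clarity, since data from subjects later found ineligible are to be kept out of pooling with eligible subjects.

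**Working it through.** **1. Which rule governs which output.**

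| SAP section | Output | Eligibility text named |
|---|---|---|
| 9.1 | ITT set, primary test | angiographic criteria only |
| 9.3 | per-protocol set | all criteria, no revision |
| 11.2 | violation count | inclusion/exclusion criteria, no revision |
| 11.3 | eligibility listing | rev 05, sections 6.2 and 6.3 |
| 13.4.3, Table 3 | primary outcome by enrolment revision | does not assess eligibility |

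Only 11.3 names a revision. No section says that the 11.3 listing feeds 9.3 or 11.2, so the effect on those two is conditional.

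**2. Possible directions, for each amended criterion.**

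- Rev 05 stricter than rev 03: a correctly enrolled rev 03 subject can fail the rev 05 list and be counted as ineligible.
- Rev 05 looser than rev 03: a rev 03 subject who broke the rule in force can pass the rev 05 list and be counted as eligible.
- Change of wording only: no subject changes status.

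The rev 03 text is not in the documents, so none of these can be ruled out, and the two criteria may differ.

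**3. The plan's own figure.** Inputs from SAP section 7: n = 176, limit 0.56, assumed rate 0.68, one-sided exact binomial test at 0.025. The smallest r with P(X ≥ r | 176, 0.56) ≤ 0.025 is 112 (exact level 0.0240). The power is P(X ≥ 112 | 176, 0.68) = 0.906. The stated 176 subjects and at least 90% power are reproduced, and this point does not dispute them.

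**4. Illustration of size, in both directions.** These are assumptions: a per-protocol set that should hold 176 subjects with 120 successes (0.68 × 176 = 119.7), from which k subjects are wrongly removed. The rate lies between (120 − k)/(176 − k), if all k were successes, and 120/(176 − k), if all k were failures. The starting rate is 120/176 = 68.2%.

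| k | Set size | All k successes | All k failures | Successes needed | Power at 0.68 |
|---|---|---|---|---|---|
| 2 | 174 | 118/174 = 67.8% | 120/174 = 69.0% | 111 | 0.897 |
| 4 | 172 | 116/172 = 67.4% | 120/172 = 69.8% | 110 | 0.888 |
| 9 | 167 | 111/167 = 66.5% | 120/167 = 71.9% | 107 | 0.879 |
| 18 | 158 | 102/158 = 64.6% | 120/158 = 75.9% | 102 | 0.844 |

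The successes needed come from the same exact test at the smaller size. Even at the low end of each row the count reaches the number needed, and with 18 removed it only just does (102 against 102).

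The same figures serve for the reverse error. If a set of 176 wrongly keeps k subjects, 68.2% is reported where the correct rate lies in the range shown.

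For primary safety, assume 10/176 = 5.7% with an event. Wrongly removing 2 gives 8/174 = 4.6% to 10/174 = 5.7%. Wrongly removing 9 gives 1/167 = 0.6% to 10/167 = 6.0%.

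**The case against.** The strongest reply is that 11.3 is one sentence planning a descriptive listing. It defines no violation and builds no analysis set. Under Protocol 10.2 violations are reported on forms, and Protocol 5.3 has eligibility confirmed by the investigator and the study monitor. Those judgements would naturally be made against the protocol the site was working under. The SAP also lists rev 03 among the documents reviewed, and 13.4.3 compares the primary outcome by revision. Finally, SAP 9.3 presents the per-protocol results only as context for the ITT results.

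Much of this stands. It shows that misclassification in the per-protocol set and the violation count is possible but not laid down. It does not rescue the listing, which is tied to rev 05 in so many words, and it does not supply the missing revision in 9.3 and 11.2. Comparing outcomes by revision does not establish who was eligible.

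A reader might infer more in three ways, and the documents do not support any of them.

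- *That rev 03 subjects will be dropped from the per-protocol set.* No section links the listing to that set.
- *That the error flatters the device because higher-risk subjects would be removed.* Without the rev 03 text, nothing shows which way either criterion moved.
- *That the Table 3 subgroup with SBP above 220 or DBP above 120 at enrolment, the level in rev 05 exclusion 15, shows that such subjects were eligible under rev 03.* Subgroups are run in the ITT and Treated Set populations. The first depends on angiographic criteria and the second ignores eligibility, so the subgroup could simply hold violators.

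**Conclusion.** The point holds in a limited form. The 11.3 listing uses the wrong reference text for rev 03 subjects on two criteria; that follows directly from the SAP. The violation count and the per-protocol efficacy and safety results are exposed only if the same list is used for them, which the SAP neither says nor prevents.

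The size is unknown: the documents give neither the number of rev 03 subjects affected nor the rev 03 wording. Under the assumptions above, the per-protocol efficacy rate could be off by about a point with 2 subjects misclassified and by several points with 9, in either direction. In none of the removal cases shown did the comparison with 0.56 change. The primary ITT test is not affected, because neither amended criterion is an angiographic one. The matter is worth settling because the per-protocol set is a pre-specified population and its definition should not be left to the programmer.

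**What to change.** State in SAP 9.3, 11.2 and 11.3 that each subject's eligibility is judged against the protocol revision under which that subject was enrolled. Derive one eligibility flag on that basis, and build both the per-protocol set and the count of eligibility violations from it. Present the 11.3 listing separately for rev 03 and rev 05 subjects, citing the criteria of each, and append the rev 03 text of the two amended criteria. If a view of the whole cohort against rev 05 is wanted, give it as a labelled supplementary listing that feeds no analysis set.

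The cost is a few lines of SAP text and one derived variable. The enrolment revision is already needed for 13.4.3, so no new data are required, and no clinical rule or primary analysis changes.

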12.1 Demographics

The following will be considered demographic variables, and will be presented in a summary table as follows:

- Age (mean (standard deviation))
- Sex (male/female; n, %)
- Ethnicity (Hispanic or Latino; n, %)
- Race (per category; n, %)

12.2 Prior and Concurrent medications

Prior and Concurrent medications are recorded in the Concomitant Medications Log on the General form of the eCRF. For each one of the medications, summaries will be provided for the number of times the medication was reported at baseline and during the study period (counts and %).

12.3 Baseline and Screening Conditions

The modified Rankin Scale (mRS) is a scale for measuring the degree of disability or dependence in the daily activities of people who have suffered a stroke or other causes of neurological disability. At screening, an historical mRS will be obtained from the subject or the subject's caretaker. It is an inclusion criterion that the subject has a pre-ictal mRS score of 0 or 1. One of the secondary endpoints of the study is a good clinical outcome, which is judged to be an mRS score of ≤ 2 at 90(+/-14) days.

The National Institutes of Health Stroke Scale, or NIH Stroke Scale (NIHSS) is a tool used to objectively quantify the impairment severity caused by a stroke. The NIHSS is composed of 11 items, each of which scores a specific ability between 0 (normal function) and 4 (highest level of impairment). The maximum and minimum possible scores are 42 and 0, respectively. It is an inclusion criterion that the subject has a NIHSS score of between 8 and 25 (inclusive). One of the secondary endpoints is neurological deterioration, which is defined by an increase of 4 points or more on the NIHSS score, at the 24-hour time point.

All baseline and screening variables, including medical history and current medication are listed below. They will be summarised in a table along with the demographic variables.

- NIHSS Score
 - Mean (standard deviation)
 - median (range)
 - ≤ 17 (%)
- Pre-stroke modified Rankin Scale
 - Median (range)
 - 2 or better
- Body-mass index
 - Mean (standard deviation)
- Intravenous rt-PA failure (n, %)
- Medical History (n, %, per term)
 - Hypertension
 - Diabetes mellitus
 - Dyslipidaemia
 - Current or ex-smoker
 - Atrial fibrillation
 - Previous MI/ CAD
- Neurological History (n, %, per term)
 - Previous Stroke/ TIA
- Core lab assessed Most proximal occlusion location (n, %, per term)
 - Internal carotid artery
 - M1 middle cerebral artery

- M2 middle cerebral artery
- Posterior circulation
- Other
- Occlusion side (left) (n, %)
- Largest occluded vessel size (mm; mean (standard deviation))
-

13 Efficacy Analyses

13.1 Primary Efficacy Endpoint

The primary efficacy endpoint of this prospective, multi-center, open-label study is revascularization measured using modified Thrombolysis in Cerebrovascular Infarction (mTICI inclusive of the 2c rating). The endpoint will be extracted from the data inputted by Imaging Core Laboratory Intrinsic imaging following all adjudications being completed in the Imaging consensus section of the eCRF.

Successful achievement of the endpoint is defined as achieving an mTICI score of 2b or greater in the target vessel, following 3 or less passes of the EmboTrap device and without the use of rescue therapy prior to taking the assessment angiogram (as defined in CIP002 rev 05) in the patient. Use of rescue therapy, prior to taking the primary endpoint angiogram, is a protocol violation and the resultant angiogram outcomes will be considered failures to achieve the primary endpoint irrespective of mTICI score.

The study objective is to investigate the performance of the EmboTrap device ($P_{EmboTrap}$) against a Performance Goal for efficacy ($PGefficacy$). In order to claim non-inferiority against an efficacy driven PG, the lower bound of a (95%) confidence interval must be shown to be greater than a non-inferiority limit (NL) which is the predetermined $PGefficacy$.

The $PGefficacy$ has been derived from a meta-analysis of revascularization efficacy rates from approved predicate devices' adjudicated performances as reported in the literature.

The meta-analysis involved a Bayesian hierarchical random effects model with a binomial response and logit link function using the efficacy results of all 3 devices in the TREVO 2 and SWIFT studies [1, 2]. Normally distributed random effects for study and arm within study effect were included on the linear predictor function. Only patients from within each study (TREVO 2 and SWIFT) and within each arm were thus treated as exchangeable. A normal prior on the log-odds centred on 0 and uniform prior for the random effect variances were used.

The test for non-inferiority for performance will be based on a one-sided test (at the 0.025 significance level) for a binomial proportion with hypotheses:

$$H_0: P_{EmboTrap} \leq NL \text{ versus } H_1: P_{EmboTrap} > NL$$

Thus the tested non-inferiority hypothesis will relate to the superiority of the EmboTrap device to a non-inferiority limit.

An equivalent testing procedure is available by using the sample data to calculate a confidence interval for the population proportion ($P_{EmboTrap}$). Demonstrating non-inferiority for efficacy necessitates rejecting the null hypothesis in favour of the alternative hypothesis, in this case based on the lower limit of a 95% confidence interval for a population proportion. The evaluable sample in the ARISE II trial are assumed to be representative of the population of interest and from which participants for the TREVO 2 and SWIFT trials were sampled. It is assumed that revascularization outcomes are independent of each other, such that no clinical site effect needs to be accounted for which would inflate the standard error

and confidence intervals of the proportion estimate. This assumption will be assessed as described in Section 13.3.

Estimates of each population parameter of interest for all other endpoints will be provided using appropriate confidence intervals.

The primary efficacy endpoint will be examined for the ITT population and the mITT population, the per protocol population and the Treated Set (described in Section 9) though the primary analysis will be for the ITT population.

